5.3.3.3 Serious adverse events

Summary of SAEs and TEAEs leading to treatment change:

- All treatment-emergent SAEs by primary SOC and PT.
- TEAEs leading to study drug permanently discontinued by primary SOC and PT, defined as those AEs with action taken of treatment 'drug withdrawn'.

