6.4. Dosing Modifications

The sentinel cohort of 12 patients will undergo blinded safety review by the Safety Committee 7 to 10 days after all ongoing patients in the sentinel cohort have completed

the respective dose of study medication and will determine the decision to continue at that dose into the expanded cohort. Safety will be assessed in the sentinel cohort before each dose is administered to the expanded cohort. If any of the Stopping Rules in Section 7.1.1 are met in one or more patients in the sentinel cohort and the event(s) is deemed possibly or probably related to HepTcell, dosing will be suspended pending DMC review. DMC recommendations may include instituting modifications to ensure the safety of continued dosing or discontinuing the study. If none of the Stopping Rules (below) are met, randomization and dosing may continue in the expanded study cohort. Patients will be unblinded as necessary to assess the relationship between the study medication and events that meet criteria for Stopping Rules. Patients who experience events that meet criteria for Stopping Rules will permanently terminate dosing.

Monitoring and dosing rules for patients who experience liver abnormalities is described in Section 4.1.

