7.1.1. Stopping Rules

In consultation with the DMC, the following Stopping Rules will be applied:

- ALT or AST $\geq 10 \times ULN$
- INR ≥ 1.3
- Total bilirubin $\geq 1.5 \times \text{ULN}$ (excluding patients with Gilbert Syndrome)
- Direct bilirubin $\geq 1.5 \times \text{ULN}$ (for patients with Gilbert Syndrome)
- SAEs
- Severe systemic reactogenicity event (see Appendix 1)

If any of the Stopping Rules are met in one or more patients in the sentinel cohort (ie, the first 12 patients dosed) and the event(s) is deemed possibly or probably related to study medication, dosing will be suspended pending DMC review. Similar procedures will be

applied if 2 or more patients in the sentinel or expanded study cohort together experience Stopping Rules deemed possibly or probably related to study medication at any time during the 24-week Treatment Period. DMC recommendations may include instituting modifications to ensure the safety of continued dosing or discontinuing the study.

If the study is halted based on a DMC decision or safety concern, the trial will only be restarted after notification of the competent authority via a substantial amendment.

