8.3. Safety Assessments

8.3.1. Reactogenicity Assessments

Each patient will record local events, systemic events, and oral temperature in a diary daily for 7 days after each dose. Diaries will be distributed to patients at each dosing visit to record these events. Patients will also be provided thermometers for daily recording of temperatures and measuring devices for the recording the size of injection reactions. Events will be graded according to the FDA Guidance for Industry: Toxicity Grading Scale for Healthy Adult and Adolescent Volunteers Enrolled in Preventive Vaccine Clinical Trials [United States Food and Drug Administration 2007]. Unsolicited events reported by the patients outside of this 7-day reporting period will be recorded as AEs.

Microscopic hematuria will be assessed by urinalyses performed at the visits 7±2 days after Doses 1 and 2 of study medication, and after Doses 3, 4, 5, and 6 as per the Schedule of Events (Table 1).

Reactogenicity events will be categorized separately from AEs unless they are assessed as serious, in which case they will be reported as SAEs. A list of solicited reactogenicity events is provided in Appendix 1.

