9.3. Assessment of Adverse Events

9.3.1. Severity

The Investigator should assess the severity of each AE. The AE will be recorded at its highest severity grade.

The severity of all AEs, both serious and non-serious, will be assessed by assigning a grade according to the FDA Guidance on the Toxicity Grading Scale for Preventive Vaccine Clinical Trials [United States Food and Drug Administration 2007]. NCI CTCAE, v 5.0 (http://ctep.cancer.gov/protocolDevelopment/electronic applications/ctc.htm) will be used for AEs not described in this guidance.

When an AE cannot be graded by the aforementioned FDA guidance or CTCAE, the following severity grading may be used:

- Grade 1 (Mild): awareness of sign or symptom, but easily tolerated
- Grade 2 (Moderate): discomfort enough to cause interference with usual activity
- Grade 3 (Severe): incapacitating with inability to work or do usual activity

- Grade 4 (Life-Threatening): refers to an event in which the patient was, in the view of the Investigator, at risk of death at the time of the event. (This category is not to be used for an event that hypothetically might have caused death if it were more severe.)
- Grade 5 (Fatal): death related to AE

An AE that is assessed as severe should not be confused with an SAE. Severity is a category for rating the intensity of an event, and both non-serious AEs and SAEs can be assessed as severe. An event will be defined as serious when it meets one of the criteria described in Section 9.1.7.

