5.2 Patient disposition

5.2.1 Patient disposition and withdrawals

This section describes patient disposition.

Screened patients include all patients who signed the informed consent form and are entered into the clinical database.

Re-screened patients include all patients who were declared screening failures at their first screening but were screened in a subsequent requalification.

Randomized patients will include all patients who were provided a treatment assignment that was recorded in the interactive response technology database, regardless of whether the treatment kit was used.

For patients' study status, the total number and percentage of patients in each of the following categories will be presented in the CSR using a flowchart diagram or summary table:

- Screened patients
- Re-screening patients among screened patients.
- Screen failure patients.
- Nonrandomized but treated patients (if applicable).
- Randomized patients.
- Randomized but not treated patients (if applicable).
- Patients in the mITT Population.
- Patients in the Safety Population.
- Patients in the PP Population.
- Patients who discontinued study treatment early, including primary reason for discontinuation.
- Patients who discontinued study early, including primary reason for discontinuation.

For all categories of patients (except for the screened and nonrandomized categories) the summaries will be provided by randomized treatment arms, and percentages will be calculated using the number of randomized patients as the denominator.

The number (%) of patients in each population will also be summarized by treatment. They will also be listed. The number of mis-stratified patients will be listed.

A listing of patients with population assignment including individual reasons of exclusion from the respective analysis populations will be provided. Data listing for early termination reasons will be also provided.

22-Apr-2024

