5.3.3.7 Reactogenicity Events

Each patient will record local events, systemic events, and oral temperature in a diary daily for 7 days after each dose. Incidence of reactogenicity events will be analyzed by treatment arm and dose number.

The number of patients with injection site reactogenicity events and each of the solicited events (Redness, Swelling or hardening, Pain at injection site (without pressure), tenderness) as well as with systemic reactogenicity events and each of the solicited events (fatigue, fever, chills, headache, muscle aches, joint aches, nausea, vomiting, diarrhoea) will be shown.

Also, number of events will be estimated for grouped injection site reactogenicity events (Redness, Swelling or hardening, Pain at injection site (without pressure), tenderness) and grouped systemic reactogenicity events (fatigue, fever, chills, headache, muscle aches, joint aches, nausea, vomiting, diarrhoea). Each event will be counted once by day of registration in the patient's diary card (i.e.: if the same event is registered for 3 different days in the diary card of a specific dose, 3 events will be counted for that dose).

Summaries will be performed for All events and also according to the grade Mild, Moderate and Severe. The size of reaction for Redness and Swelling (or hardening) will be assigned with the measurement in cm, being Mild from 2.5 to 5, Moderate larger than 5 to 10 and Severe larger than 10. Patients may have self reported events under 2.5 cm as an event, but following formal guidance these will not be reported as reactogenicity event in the statistical analysis.

A listing of all events recorded in the diary card will be included.

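### If a non-serious severe systemic reaction ends dosing, the SAP's counts of discontinuation for adverse events would generally miss it

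*SAP*

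**What the plan says.** **Reaction and dosing.** One of the six Stopping Rules in protocol 7.1.1 is "Severe systemic reactogenicity event (see Appendix 1"; it carries no condition on seriousness. Protocol 6.4 gives the consequence: "Patients who experience events that meet criteria for Stopping Rules will permanently terminate dosing". SAP 5.3.16 repeats that sentence.

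**Reaction and adverse-event status.** Protocol 8.3.1 states: "Reactogenicity events will be categorized separately from AEs unless they are assessed as serious, in which case they will be reported as SAEs". SAP 4.3 has the same rule. Protocol 9.3.1 separates severity from seriousness: "An AE that is assessed as severe should not be confused with an SAE".

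**Counting discontinuations.** SAP 5.3.3.3 plans a table of "TEAEs leading to study drug permanently discontinued by primary SOC and PT, defined as those AEs with action taken of treatment" recorded as withdrawal of the drug (Table 14.3.2.2). The overview in SAP 5.3.3.2 (Table 14.3.1.1) has a line for TEAEs leading to permanent discontinuation, and Listing 16.2.7.3 gives the individual cases.

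**Reporting reactions.** SAP 5.3.3.7 says: "Incidence of reactogenicity events will be analyzed by treatment arm and dose number". It adds: "Summaries will be performed for All events and also according to the grade Mild, Moderate and Severe".

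**Disposition.** SAP 5.2.1 tabulates by arm "Patients who discontinued study treatment early, including primary reason for discontinuation".

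**The concern.** Two conventions, each reasonable alone, do not fit together. Keeping solicited reactions out of the adverse-event data is one. Counting discontinuations for harm from adverse events only is the other. Combined, they leave one of the protocol's own mandatory reasons for ending dosing outside every planned output on events leading to discontinuation.

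At stake is how the safety results read. Safety is a secondary objective, the regimen is six doses of an adjuvanted product compared with saline, and SAP section 2 already describes HepTcell as well tolerated. Someone checking that description would look at the discontinuation line of the TEAE overview. A zero there could mean that nobody stopped because of a reaction, or that anyone who did was classified elsewhere. The planned tables do not let the reader tell these apart.

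**Working it through.** The plan states no figure on this point, so there is none to reproduce. The check is a cross-reading, followed by arithmetic for scale only.

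**Step 1: follow one patient.** Suppose a patient has a severe, non-serious solicited systemic reaction within the 7-day diary period.

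| Question | Source | Answer |
|---|---|---|
| Is a Stopping Rule met? | Protocol 7.1.1 | Yes |
| Does dosing end? | Protocol 6.4; SAP 5.3.16 | Yes, permanently |
| Must the event be serious? | Protocol 9.3.1 | No |
| Is it classed as an AE? | Protocol 8.3.1; SAP 4.3 | No, because it is not serious |
| Is it in the TEAE discontinuation outputs? | SAP 5.3.3.2, 5.3.3.3; Tables 14.3.1.1, 14.3.2.2; Listing 16.2.7.3 | No, because these draw on AEs |
| Is it in the reactogenicity table? | SAP 5.3.3.7; Table 14.3.5.1 | Yes, by arm, dose and grade, but not linked to the end of dosing |
| Is the patient in disposition? | SAP 5.2.1 | Yes, with a primary reason whose categories are not given |

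**Step 2: is the gap specific to this rule?** Yes. The other five Stopping Rules are SAEs and four laboratory criteria. SAEs are AEs, and protocol 9.4 records clinically significant laboratory abnormalities as AEs. Solicited systemic reactogenicity is the one criterion that the documents expressly divert from the AE data.

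**Step 3: is there another way in?** There is one partial route. Protocol 8.3.6 records clinically relevant changes in vital signs as AEs and names fever among the significant changes. Fever is also a solicited systemic event in protocol Appendix 1. A fever could therefore be entered as an AE, and the documents do not say which rule prevails.

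**Step 4: scale.** The planned size is 40 per arm (protocol 10.2).

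- Each omitted patient: 1/40 = 2.5 percentage points of that arm's rate.
- Expected omissions in an arm: 40 × p.
- Chance of at least one in an arm: 1 − (1 − p)^40.

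Here p is the per-patient probability of a non-serious severe systemic reaction. The documents do not give it, so the values below are assumptions.

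| Assumed p | Expected omissions per arm | Chance of at least one |
|---|---|---|
| 1% | 0.4 | 33% |
| 2% | 0.8 | 55% |
| 5% | 2.0 | 87% |
| 10% | 4.0 | 99% |

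**The case against.** The strongest reply is that nothing is lost. SAP 5.2.1 counts every early treatment discontinuation by arm with its reason. SAP 5.3.3.1 shows how many patients reached each dose, and SAP 5.3.3.7 shows severe reactions by arm and dose. Listings of next-dose eligibility (16.2.1.2.2), treatment completion (16.2.5.1) and diary events (16.2.9.1) would let a reader reconstruct a case. Table 14.3.2.2 delivers what its title promises, and discontinuation for intolerance is not a listed safety endpoint. All of this stands. What is missing is the link between reaction and end of dosing, and a summary by arm; listings do not supply that summary.

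Three stronger readings are tempting, and the documents support none of them.

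- *Such a patient appears in no table as having stopped for harm.* Protocol 7.1 and SAP 2.3.2 list patient request, noncompliance, loss to follow-up, investigator discretion and sponsor request. These are introduced as reasons for which patients could be discontinued, and they are not shown to be the disposition code list. They omit adverse events altogether, although the SAP plans to tabulate AE withdrawals. The label such a case would receive is unknown.
- *Discontinuations for tolerability are in fact undercounted.* No count of these events is given. Some severe reactions might also be judged serious under the criteria in protocol 9.1.7 and so reach the AE data.
- *The omission favours HepTcell.* An excess of reactions in an adjuvanted arm is plausible but not shown. The Phase 1 summary in protocol 1.3 reports no effect of dose level, number of doses or adjuvant on any safety parameter. Its only trend was in injection-site reactions in the high-dose adjuvanted group, none of them severe. The present trial uses the lower peptide dose, though with six doses instead of three.

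**Conclusion.** The point holds as a conditional gap in the safety outputs. If a non-serious severe systemic reaction ends a patient's dosing, the AE-based discontinuation tables and listing would generally not show it, and no other planned summary is shown to identify it as a stop for harm. Total discontinuations remain correct.

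Each such patient is 2.5 percentage points at the planned 40 per arm. The number of patients and the direction between arms cannot be determined from the documents. The conclusion assumes that the classification rule is applied as written, and it leaves open the fever overlap between protocol 8.3.1 and 8.3.6. This does not show that the tolerability conclusion is wrong. It is a worthwhile correction because the cause omitted is one that the protocol itself makes mandatory and because the remedy is cheap.

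**What to change.** - Keep the TEAE discontinuation row as now defined. In SAP 5.3.3.2 and 5.3.3.3 and in Tables 14.3.1.1 and 14.3.2.2, add a by-arm row *solicited reactogenicity event leading to permanent discontinuation* and a combined *TEAE or reactogenicity event* total, counting each patient once in the total.
- In SAP 5.2.1, state the categories of primary reason for treatment discontinuation and include *adverse event / reactogenicity / Stopping Rule*.
- Derive both from the next-dose eligibility, treatment-completion and diary data already planned for listing.
- Reconcile protocol 8.3.1 with 8.3.6, so that it is clear how a solicited fever is classified for these tables.

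The cost is SAP wording, one or two extra table rows and one disposition category. The SAP addendum already supplements the Week 24 outputs, so there is a place for it; if added now, the rows should be marked as specified after that analysis. The discontinuation figure may become slightly less favourable. If the count is zero, the new row says so and supports the tolerability statement. No clinical rule changes.

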5.3.3.4 Medically-Attended AEs (MAEs)

Number and percentage of patients with MAEs will be reported by primary SOC and PT by treatment arm. These will be assessed separately for the Day 169 Treatment Period and Day 505 Follow-Up Period.

5.3.3.5 New-onset Chronic Illnesses (NCIs)

Number and percentage of patients with NCIs will be reported by primary SOC and PT by treatment arm. These will be assessed separately for the Day 169 Treatment Period and Day 505 Follow-Up Period.

5.3.3.6 Immune-mediated Medical Conditions (IMCs)

IMCs will be analyzed as recorded on the eCRF. Number and percentage of patients with IMCs will be reported by primary SOC and PT by treatment arm.

These will be assessed separately for the Treatment Period up to Day 169 and the Follow-Up Period up to Day 505.

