3.4. Safety Endpoints

- Incidence and severity of AEs, medically-attended AEs (MAEs), new-onset chronic illnesses (NCIs), and immune-mediated medical conditions (IMCs)
- Incidence and severity of local and systemic reactogenicity events
- Incidence and duration of hepatitis flares, defined as alanine aminotransferase (ALT) \geq 3 × upper limit of normal (ULN) and \geq 100 U/L
- Changes in ALT, aspartate aminotransferase (AST), alkaline phosphatase (AP), gamma glutamyl transferase (GGT), bilirubin total and direct, international normalized ratio (INR) and other laboratory parameters

Safety endpoints will be assessed separately for the 24-week Treatment Period and 52-week Follow-Up Period.

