- ^a Randomization may occur up to 3 working days before Day 1 (the day of first dosing) to allow for the possible preparation of study medication by a central pharmacy and shipment to the study site. If the patient is to be randomized before Day 1, the eligibility of the patient will be confirmed by a telephone visit prior to randomization. Concomitant medications AEs will also be assessed.
- b If a patient prematurely discontinues study medication before Day 169, Day 169/Early termination procedures will be performed. Patients who prematurely discontinue study medication will remain in the study for Follow-Up Period study assessments, the dates of visits adjusted to correspond to 13, 26, 39 and 52 weeks after the last dose of study medication.
- ^c A telemedicine visit would include a home visit by appropriate trained personnel to perform a target and symptom-driven physical and obtain vital signs and safety laboratories. The remaining portions of the visit may be conducted virtually by the study investigator.
- d After Day 169 or ET, only immunosuppressive medications, vaccines, and new HBV treatments or medications associated with MAEs, NCIs, SAEs, hepatitis flares, or hepatic injury will be recorded.
- ^e Measured before any blood sample collection.
- f Not required if performed within 12 months or if no fibrosis seen on liver biopsy within 2 years before screening.
- g For women of childbearing potential only. A serum pregnancy test will be obtained in lieu of a urine pregnancy test at screening.
- h Hepatitis B genotyping will be performed at screening if it has not been documented in the prior medical record.
- ¹ Serology and viral markers = HBsAg, anti-HBs, HBVDNA, pg-RNA, HBcAg, HBeAg, HBeAg antibody.
- Jif the patient has experienced an acute illness or temperature > 38°C in the 2 days prior to dosing, the administration of study medication and corresponding visit will be delayed until the illness or fever has resolved.
- k Investigators will review the eligibility of all patients to determine if the next treatment is to be administered. Eligibility for the next treatment will include 1) confirmation that patients did not meet a Stopping Rule (Section 7.1.1); 2) confirmation that the pre-treatment liver parameters are within acceptable ranges for treatment (Section 4.1); 3) confirmation that patients do not have a new confirmed or suspected IMC (Appendix 2). Patients not meeting these criteria will not be treated.

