- 1 If an authorized COVID-19 vaccine has been administered in proximity to a scheduled IP administration, a ± 3 day window is allowed for IP dosing.
- ^m After Day 169 or ET, only MAEs, NCIs and IMCs will be recorded.
- ⁿ A single blood sample will be collected for biobanking at the beginning of the study (prior to dosing on Day 1) and end of the study. This sample will be used for future analyses not specified in the protocol. Analysis will be limited to HBV serologic and HBV-specific DNA and RNA and patients' DNA will not be analyzed.
- ° Safety laboratory testing, including liver panel, for Doses 1 and 2 will be obtained during the visits conducted 7±2 days after these doses of study medication. Safety laboratory testing following Doses 3, 4 and 5 will be obtained in the interval from 7 days after dose administration and before the next dose of study medication is administered. Safety labs after Dose 6 will be assessed at the Day 169 visit.
- ^p Diaries will also be reviewed at the Day 85, Day 113, Day 141 and Day 169 visits

Table 2 Schedule of Events – Follow-up Period

	Follow-Up Period					
Study Visit	Day 232	Day 323	Day 414	Day 505 or ET ^a		
Completion of Week (number)	33	46	59	72		
Window (days)	±10 days	±10 days	±10 days	±10 days		
Visit may be conducted at home or work or in part as a telemedicine visit ^b	X		X			
Immunosuppressive medications, vaccines, and new HBV treatments (only) ^c	X	X	X	X		
Targeted and symptom-driven PE	X	X	X	X		
Height and weight				X		
Vital signs ^d	X	X	X	X		
ECG ^d				X		
Hematology and serum chemistry	X	X	X	X		
Liver panel	X	X	X	X		
HBV serology and viral markers ^e		X		X		
Whole blood for PBMC isolation		X		X		
MAEs, NCIs and IMCs (only) ^f	X	X	X	X		

AE = adverse event; ECG = electrocardiogram; ET = early termination; HBV = hepatitis B virus; HIV = human immunodeficiency virus; MAE = medically-attended adverse event; NCI = new-onset chronic illness; IMC = immune-mediated medical condition; PBMC = peripheral blood nonnuclear cell; PE = physical examination.

^a If a patient prematurely discontinues study medication before Day 505, Day 505/Early termination procedures will be performed.

^b A telemedicine visit would include a home visit by appropriate trained personnel to perform a target and symptom-driven physical and obtain vital signs and safety laboratories. The remaining portions of the visit may be conducted virtually by the study investigator.

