9.2. Reporting Responsibilities and Periods

It is the responsibility of the Investigator or Subinvestigator(s) to perform periodic assessment of AEs. AEs spontaneously reported by the patient or reported in response to an open question from the study personnel (eg, 'Have you had any health problems since the previous visit/you were last asked?') or revealed by observation will be recorded.

AEs and concomitant medications will be recorded from the signing of informed consent to Day 169, but only MAEs, NCIs, and IMCs, which will be categorized as AEs, will be followed subsequently through Day 505. Concomitant medication collection will align with AE collection. The AE term, date of AE onset, date of AE resolution (if applicable), severity, causality, action taken for the AE, outcome and whether or not the AE is an MAE, NCI, and or SAE will be recorded.

AEs must be monitored until they are resolved or stabilized, are clearly determined to be due to a patient's stable or chronic condition or intercurrent illness(es), or follow-up is no longer possible. Data describing AEs will be recorded in the patient's medical record and as appropriate, an SAE report form. SAEs will be reported to the Sponsor as described in Section 9.7.

Any SAE that the Investigator considers to be possibly or probably related to study medication and occurs at any time after completion of the study must be reported to the Sponsor or designee. If at the time the Investigator initially reports an SAE, the event has not resolved, the Investigator must provide a follow-up report as soon as it resolves (or upon receipt of significant information if the event is still ongoing).

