Appendix 2 – Immune-Mediated Medical Conditions

Any AE assessed by the Investigator as immune-mediated but not appearing in the list below will also be reported as an IMC.

Gastrointestinal disorders

- Celiac disease
- Crohn's disease
- Ulcerative colitis
- Ulcerative proctitis

Liver disorders

- Autoimmune cholangitis
- Autoimmune hepatitis
- Primary biliary cholangitis
- Primary sclerosing cholangitis

Metabolic diseases

- Addison's disease
- Autoimmune thyroiditis (including Hashimoto thyroiditis)
- Diabetes mellitus type I
- Grave's or Basedow's disease

Musculoskeletal disorders

- Antisynthetase syndrome
- Dermatomyositis
- Juvenile chronic arthritis (including Still's disease)
- Mixed connective tissue disorder
- Polymyalgia rheumatic
- Polymyositis
- Psoriatic arthropathy
- Relapsing polychondritis
- Rheumatoid arthritis
- Scleroderma, including diffuse systemic form and CREST syndrome
- Spondyloarthritis, including ankylosing spondylitis, reactive arthritis (Reiter's Syndrome) and undifferentiated spondyloarthritis

- Systemic lupus erythematosus
- Systemic sclerosis

Neuroinflammatory disorders

- Acute disseminated encephalomyelitis, including site specific variants (eg, noninfectious encephalitis, encephalomyelitis, myelitis, radiculomyelitis)
- Cranial nerve disorders, including paralyses/paresis (eg, Bell's palsy)
- Guillain-Barré syndrome, including Miller Fisher syndrome and other variants
- Immune-mediated peripheral neuropathies and plexopathies, including chronic inflammatory demyelinating polyneuropathy, multifocal motor neuropathy and polyneuropathies associated with monoclonal gammopathy
- Multiple sclerosis
- Narcolepsy
- Optic neuritis
- Transverse myelitis
- Myasthenia gravis, including Eaton-Lambert syndrome

Skin disorders

- Alopecia areata
- Autoimmune bullous skin diseases, including pemphigus, pemphigoid and dermatitis herpetiformis
- Cutaneous lupus erythematosus
- Erythema nodosum
- Morphoea
- Lichen planus
- Psoriasis
- Rosacea
- Sweet's syndrome
- Vitiligo

Vasculitides

- Large vessels vasculitis including: giant cell arteritis such as Takayasu's arteritis and temporal arteritis
- Medium sized and/or small vessels vasculitis including: polyarteritis nodosa, Kawasaki's disease, microscopic polyangiitis, Wegener's granulomatosis,

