4.3 Safety Endpoints

- Incidence and severity of AEs, medically-attended AEs (MAEs), new-onset chronic illnesses (NCIs), and immune-mediated medical conditions (IMCs)
 - An MAE is an AE resulting in hospitalization, emergency room visit, or visit to or from medical personnel (other than routine health care visits).
 - An NCI is an AE that is new (i.e., not present at baseline) and typically chronic. Because of the significance of this designation for the patient's health and for evaluation of vaccine safety, NCIs are expected to be diagnoses, not symptoms, and the Investigator should record sufficient data in the source document to support the diagnosis.
 - An IMCs is any AE appearing in the list of AEs detailed in Appendix 2 of the protocol. Any AE
 assessed by the Investigator as immune-mediated but not appearing in the list will also be
 reported as an IMC.
- Incidence and severity of local and systemic reactogenicity events
 Reactogenicity local or systemic events, and oral temperature will be recorded by the patient in a diary daily for 7 days after each dose. Events will be graded according to the FDA Guidance for

Industry: Toxicity Grading Scale for Healthy Adult and Adolescent Volunteers Enrolled in Preventive Vaccine Clinical Trials [United States Food and Drug Administration 2007].

Reactogenicity events will be categorized separately from AEs unless they are assessed as serious, in which case they will be reported as SAEs. The solicited reactogenicity events are the following:

Local (injection site) reactogenicity events:

- Pain at injection site (without pressure)
- Redness
- Swelling or hardening
- Tenderness

Systemic reactogenicity events

- Fatigue
- Fever
- Chills
- Headache
- Muscle aches
- Joint aches
- Nausea
- Vomiting
- Diarrhoea

Unsolicited events reported by the patients outside of this 7-day reporting period will be recorded as AEs.

Incidence and duration of hepatitis flares;

Hepatitis flares are defined as alanine aminotransferase (ALT) \geq 3 × upper limit of normal (ULN) and > 100 U/L.

The incidence and duration of hepatitis flares will be estimated considering ALT values across all measurements taken (scheduled and repeated) during the treatment period, as follows:

- Incidence of hepatitis flares will be estimated with the number of episodes across measurements on the treatment period per patient.

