5.3.3 Safety Analyses

Summary statistics will be provided by treatment arm and overall (if applicable) for the safety endpoints; summaries will be provided on the Safety population. Listings will also be presented.

The safety endpoints will be considered as described in section 4.3. Analyses to be performed are described in the following subsections.

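### The SAP counts immune-mediated conditions from the eCRF record with no stated check against the Appendix 2 list that defines them, so the IMC tables can undercount

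*SAP*

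**What the plan says.** Incidence and severity of IMCs is among the safety endpoints in protocol 3.4, listed beside adverse events (AEs), medically-attended events (MAEs) and new-onset chronic illnesses (NCIs).

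- **Definition.** SAP 4.3: "An IMCs is any AE appearing in the list of AEs detailed in Appendix 2 of the protocol". The sentence after it adds unlisted events that the investigator assesses as immune-mediated. Protocol Appendix 2 agrees: "Any AE assessed by the Investigator as immune-mediated but not appearing in the list below will also be reported as an IMC".
- **Link from definition to analysis.** SAP 5.3.3: "The safety endpoints will be considered as described in section 4.3".
- **Analysis rule.** SAP 5.3.3.6: "IMCs will be analyzed as recorded on the eCRF". Patients are then counted by system organ class, preferred term and arm, separately for treatment (Table 14.3.3.3.1) and follow-up (Table 14.3.3.3.2).
- **Data to record.** Protocol 9.2 lists the items for each event and ends with "whether or not the AE is an MAE, NCI, and or SAE will be recorded". IMC is not in that list.
- **Collection in follow-up.** Protocol Table 1 footnote: "After Day 169 or ET, only MAEs, NCIs and IMCs will be recorded".

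**The concern.** The definition depends on which event occurred. The analysis rule depends on how a site classified it. The two agree only if every listed event is recorded as an IMC, and no step is stated that would reveal a failure to do so: no preferred-term list, no MedDRA query and no medical reconciliation.

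Appendix 2 is long and includes conditions such as rosacea, psoriasis, Bell's palsy and Raynaud's phenomenon. A site may enter one of these as an ordinary event without thinking of the list. The event is an IMC under SAP 4.3 but would be absent from the IMC tables, and a reader of those tables could not tell that it sits elsewhere.

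The product is an adjuvanted immunotherapeutic vaccine. SAP section 2 also cites the absence of ongoing MAEs, NCIs or IMCs as the reason for ending safety follow-up at termination. Statements about IMCs should rest on the SAP's own definition.

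**Working it through.** The plan states no figure on this point, so there is none to reproduce. The check is a comparison of the text, followed by an illustration on assumed inputs.

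**Text comparison**

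1. Let D be the events that meet SAP 4.3 (on the list, or judged immune-mediated by the investigator), and R the events recorded as IMCs on the eCRF.
2. Under Appendix 2, investigator judgement adds to the list and never removes from it. Every correctly recorded IMC therefore belongs to D, so R lies within D.
3. SAP 5.3.3.6 counts R. The difference, D minus R, is the listed events not recorded as IMCs, plus any unlisted event judged immune-mediated but not recorded as one. Barring events wrongly recorded as IMCs, the error can only go downward.
4. Appendix 2 has 4 + 4 + 4 + 13 + 9 + 10 + 2 + 13 = 59 entries (gastrointestinal, liver, metabolic, musculoskeletal, neuroinflammatory, skin, vasculitides, others).
5. Protocol 9.2 names MAE, NCI and SAE status but not IMC status. How an IMC is marked on the eCRF is therefore not described there.

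**Illustration**

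Inputs: n = 40 per arm (SAP 5.1). The risk p that a patient has an IMC and the probability s that it is recorded as one are not in the documents. I assume p from 1% to 5% and s from 50% to 100%, with at most one IMC per patient.

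P(at least one patient missed in an arm) = 1 − (1 − p(1 − s))^40

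| p | s | Calculation | Result |
|---|---|---|---|
| any | 100% | 1 − 1^40 | 0% |
| 1% | 90% | 1 − (1 − 0.001)^40 | 3.9% |
| 2.5% | 80% | 1 − (1 − 0.005)^40 | 18.2% |
| 5% | 50% | 1 − (1 − 0.025)^40 | 63.7% |

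P(the arm's IMC table shows at least one patient) = 1 − (1 − ps)^40. At p = 2.5% this is 1 − 0.975^40 = 63.7% with complete recording and 1 − 0.98^40 = 55.4% with 80% recording.

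Effect of one event on a small count: 0/40 has an exact 95% upper limit of 1 − 0.025^(1/40) = 8.8% (two-sided interval). For 1/40 (2.5%) the exact upper limit is 13.2%.

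**The case against.** The strongest reply is that the two sections do different jobs: 4.3 says what an IMC is, and 5.3.3.6 says where the data come from. SAP 5.3.3 keeps the 4.3 definition in force, and 5.3.3.6 does not say that the eCRF record is the sole source. Sites are pointed to Appendix 2 repeatedly, because before each of Doses 2 to 6 the investigator must confirm that there is no new confirmed or suspected IMC. Protocol 11.5 provides validation checks and queries, and the eCRF itself, which we have not seen, may carry a pick-list. Protocol 9.2 elsewhere names IMCs among the events followed after Day 169, so the missing attribute may be a drafting gap. Through Day 169 an unrecorded event would still appear in the treatment-emergent AE tables by preferred term and in the by-patient listing. IMCs are summarised descriptively, without a hypothesis test.

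Most of this stands. A reader might infer that the SAP flatly contradicts itself. The documents do not support that, since a site that applies Appendix 2 fully produces the same count under both sections. A reader might also infer that events were in fact missed, that recording differs between sites, or that the loss favours one arm. Nothing in the documents shows any of these, and blinded classification gives no reason to expect a difference by arm.

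What the reply does not supply is a check of recorded events against the list. The pre-dose review covers Doses 2 to 6 and not the follow-up period, and the general data validation is not described as covering IMC status.

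**Conclusion.** The point holds as a missing reconciliation step. A listed event that is not recorded as an IMC can drop out of Tables 14.3.3.3.1 and 14.3.3.3.2, and the resulting count would then fall below the SAP's own definition. The direction follows from the text, provided that events are not wrongly recorded as IMCs.

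The size cannot be computed from the documents. The 3.9% to 63.7% range rests entirely on assumed risks and recording probabilities, and it is zero if recording is complete.

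The consequence is limited. Through Day 169 the event is lost from the IMC count but not from the safety data. The finding gives no ground to dispute the SAP's statements that the product was well tolerated or that no IMC was ongoing at termination. It shows only that IMC statements have no documented check against Appendix 2. The change is worth making because it is cheap and brings the analysis closer to the definition already adopted.

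**What to change.** Replace the counting rule in SAP 5.3.3.6 with a union: an event is an IMC if it is recorded as one on the eCRF, or if its MedDRA preferred term maps to a fixed term list built from Appendix 2. The eCRF arm must stay, because it alone identifies unlisted events that the investigator judged immune-mediated.

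- Fix the term list, and have any matches reviewed, by staff without access to individual treatment assignments.
- Settle cause-dependent entries, such as autoimmune thrombocytopenia, myocarditis and glomerulonephritis, by medical review under the same blinding. A preferred term alone may not show the cause.
- Tabulate the union by arm and period, with a footnote giving the number from each source.
- Add IMC to the event attributes in protocol 9.2, or state where it is captured.

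**Cost.** One term list, a small amount of medical review, a short text change and a rerun of the IMC tables. AEs are already coded in MedDRA (SAP 5.3.3.2). The addendum lists only the follow-up IMC table as a new output, so Table 14.3.3.3.1 would also need to be rerun.

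**Limit.** After Day 169 only MAEs, NCIs and IMCs are collected, so in follow-up the term match can recover only events that were collected as MAEs or NCIs.
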